- Record all prescription and nonprescription drug and supplements taken from the Week 24/Baseline visit through the Safety Follow-Up Period. Concomitant medications with start date prior to the first dose of study drug for MVT-601-3103 should be reported as concomitant medications in the parent study (MVT-601-3101 or MVT-601-3102). If concomitant medication is ongoing at the time of the first dose of study drug for MVT-601-3103, please see the Case Report Form Completion Guidelines for instructions for recording the follow-up status.
- Concomitant medications are recorded both for the parent study and for MVT-601-3103 at the Week 24/Baseline visit. (See footnote e for further details).
- This is a parent study (MVT-601-3101 or MVT-601-3102) Week 24 procedure that serves as the Week 24/Baseline procedure for MVT-601-3103 and is covered under the informed consent for the parent study.
- The indicated procedure may be performed at the Un-scheduled visit based on the purpose of the visit (eg, follow-up for an adverse event or abnormal laboratory test).
- See parent study protocols (MVT-601-3101 or MVT-601-3102) for instructions on testing visual acuity.
- The exam may include a gynecologic examination, if indicated based on signs and symptoms.
- The 12-lead ECGs will be submitted for central reading.
- Clinical chemistries will be collected at each visit. A complete blood count will be collected at Week 24/Baseline, Week 28, Week 36, and Week 52. At the Week 24/Baseline visit and Week 52 visit, additional tests include: fasting (at least 8 hours) glucose, lipid profile, and hemoglobin A1c.
- Samples should be obtained in a fasted state (at least 8 hours). Water is allowed during the fasting period.

- 
- n. For Week 24/Baseline samples, see the parent protocol (MVT-601-3101 or MVT-601-3102). At Week 52/Early Termination, collect samples for analysis of estradiol concentrations only. On days when pharmacodynamics samples are collected, administer the study treatment after the pharmacodynamics sample collections are completed.
  - o. At the Week 24/Baseline visit, transition the patient within her eDiary from the parent study to MVT-601-3103. The eDiary data collection will include NRS pain scores, menstruation information (including severity of bleeding), analgesic drug use, date and time of study drug administration, and sB&B scale scores.
  - p. Bone densitometry (L1-L4, total hip, femoral neck) will be submitted for central reading.

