Questionnaires are administered on the electronic tablet and on paper at each visit. These procedures should occur before any other types of study procedures are performed. When both electronic tablet and paper questionnaires are required at a visit, the electronic questionnaires should be done first. The order in which the electronic tablet and paper questionnaires should be administered are as follows:

- Electronic tablet questionnaires (in the order they appear in the tablet)
- Paper questionnaires
  - PGA for function
  - EHP Work Domain [Week24/Baseline and Week 52 only]

Patients will bring their eDiary, analgesic medications, and study drug to each visit. The site must document the start and stop dates of the patient's menses.

An endometrial biopsy will have been performed at the parent study Week 24 visit for all patients who participated in MVT-601-3101 (see MVT-601-3101 protocol for details). Safety monitoring for this study includes physical examination, clinical laboratory tests, pregnancy tests, and adverse event collection at each visit. Clinical chemistries will be collected at each visit. A complete blood count will be collected at Week 24/Baseline, Week 28, Week 36, and Week 52. At the Week 24/Baseline visit and Week 52 visit, additional tests include fasting (at least 8 hours, other than water) glucose, lipid profile, and hemoglobin A1c.

ECGs will be done at the Week 24/Baseline and at the Week 52/Early Termination visits. Bone densitometry will occur at the Week 24/Baseline, Week 36, and Week 52/Early Termination visits. Week 52/Early Termination.

Bone densitometry and ECGs will be submitted for central reading.

Study drug compliance will be reviewed at each visit. Fasting (other than water) for at least 8 hours is required prior to blood sampling on Week 24/Baseline and Week 52/Early Termination visits and for 1 hour after administration of the study drug in the clinic. Laboratory requisitions must indicate whether or not the patient was not fasted for their chemistry and lipid testing.

Refer to the Schedule of Activities (see [Section 1.1](#)) for information about study procedures during the Open-Label Treatment Period.

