
Phospholipidosis
 
Data from nonclinical studies in rats and monkeys showed histopathological changes consistent with phospholipidosis (PLD). PLD by itself is not adverse. No clinical evidence of relugolix-related PLD-associated toxicity has been observed nor was there a clinically meaningful increase in a biomarker of PLD assessed in phase 2 clinical studies.
	
Patients with significant underlying medical conditions are excluded.
	
Routine safety monitoring including laboratory assessments, ECGs, and assessment of adverse events, including any ophthalmologic adverse events, will be monitored during this study.

Potential Risk of Clinical Significance	Mitigation Strategy	
	Impact on Eligibility	Monitoring and Withdrawal Criteria
Metabolic Changes Metabolic changes (insulin resistance, dyslipidemia, and increased weight) with increased risk of diabetes are a potential risk of the hypoestrogenic state induced by relugolix.	Exclusion criteria for current medical history of cardiovascular disease in the parent studies.	Fasting lipids and glucose will be monitored during the study.
Reproductive Toxicity	Premenopausal compliance with specified acceptable non-hormonal contraception; exclusion of pregnant and lactating women.	Pregnancy testing at each study visit; immediate withdrawal for pregnancy.
Risk of Estradiol (1.0 mg)/Norethindrone Acetate (0.5 mg) Low-dose estradiol and norethindrone acetate are approved for the prevention of postmenopausal osteoporosis and the treatment of moderate to severe vasomotor symptoms. It is contraindicated for women with a history of breast cancer or estrogen-dependent neoplasia, history of (or active) deep vein thrombosis, pulmonary embolism, thromboembolic disease (myocardial infarction or stroke within the past year), liver dysfunction, prior hypersensitivity, and pregnancy.	Women with breast cancer or other estrogen-dependent malignances, a history of deep vein thrombosis, pulmonary embolism, thromboembolic disease, liver dysfunction, prior hypersensitivity, migraine with aura, porphyria, and pregnancy excluded from the parent studies. Physical examination, clinical chemistries, and 12-lead ECG will be performed at the Week 24/Baseline visit.	Clinical chemistries assessing liver tests, fasting glucose and lipids, and urine pregnancy tests will be performed throughout the study. Adverse events will be recorded at each visit.

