## 9.5. Safety Analyses

Safety assessments will include treatment-emergent adverse events, vital signs and weight, physical examinations, clinical laboratory tests, 12-lead ECG, and bone mineral density with DXA. Safety summaries by treatment group will be performed using treatment groups defined based on the actual randomized treatment received in the parent study.

The treatment-emergent period will be defined as the period of time from the first dose date and time of randomized study drug in the parent study through 30 days after the last dose of study drug, or the date of initiation of another investigational agent or hormonal therapy affecting the hypothalamic-pituitary-gonadal axis or surgical intervention for endometriosis, whichever occurs first. Safety will be assessed through summaries of adverse events, the frequency of treatment discontinuations due to adverse events, laboratory evaluations, and bone densitometry results.

The severity of all adverse events is to be evaluated by the investigator based on the National Cancer Institute CTCAE. All adverse events will be coded to preferred term, high level term, and system organ class using MedDRA 20.0 or higher. The incidence of adverse events will be presented by MedDRA system organ class and preferred term, relationship to study drug treatment, and severity. A patient reporting the same adverse event more than once is counted once, and at the maximum severity or strongest relationship to study drug treatment when calculating incidence.

Laboratory data consist of chemistry, hematology, and hormonal tests. Only data collected by the central laboratory will be used to do the analyses. The National Cancer Institute CTCAE will be used to categorize toxicity grade for the laboratory parameters. Shift tables will be provided for each gradable parameter to summarize baseline toxicity grade versus post-baseline toxicity grade. For laboratory parameters that are not gradable by the CTCAE, a shift table based upon the normal range (low, normal, and high) will be provided for each parameter to summarize the parent study Baseline versus post-baseline results. All data will be listed and summarized by visit. The change from parent study Baseline to each post-baseline study visit will be presented by parent study treatment group for each laboratory test.

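### Section 9.5 compares and grades glucose at every visit without regard to fasting state, although an 8-hour fast is required only at Week 24/Baseline and Week 52/Early Termination

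*Protocol*

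**What the plan says.** Section numbers refer to Amendment 1, the latest version whose Section 9.5 is in the pages available. The same rules stand in the original protocol.

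- **Collection.** Table 1-1, footnote l: "Clinical chemistries will be collected at each visit". Table 6-1 lists glucose in its Chemistry column.
- **Fasting.** The same footnote continues: "At the Week 24/Baseline visit and Week 52 visit, additional tests include: fasting (at least 8 hours) glucose, lipid profile, and hemoglobin A1c". In the clinical laboratory row of Table 1-1, the fasting footnote (m) is attached only to the Week 24/Baseline and Week 52/Early Termination cells. Section 6.2 agrees: "Fasting (other than water) for at least 8 hours is required prior to blood sampling on Week 24/Baseline and Week 52/Early Termination visits".
- **Recording.** Section 6.2 also has fasting status documented: "Laboratory requisitions must indicate whether or not the patient was not fasted for their chemistry and lipid testing".
- **Analysis.** Section 9.5 sets the rule for the laboratory summaries: "The change from parent study Baseline to each post-baseline study visit will be presented by parent study treatment group for each laboratory test". On grading it says: "Shift tables will be provided for each gradable parameter to summarize baseline toxicity grade versus post-baseline toxicity grade". Neither sentence mentions fasting.
- **Purpose.** Table 7-2 names insulin resistance and diabetes as potential risks and gives the monitor: "Fasting lipids and glucose will be monitored during the study". Its row on estradiol/norethindrone acetate goes further and has fasting glucose and lipid tests done throughout the study.

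**The concern.** Glucose depends on recent food intake, so a fasted and a fed value are not the same measurement. If the summary compares them directly, the by-visit change from Baseline carries a component that follows the sampling rule. It can appear after Week 24, when the fasting rule lapses, and disappear at Week 52, when it returns. The same component can push some Week 28 to 48 and Follow-Up values into a higher grade in the shift tables.

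Glucose is the stated monitor for a named metabolic risk. In a single-arm extension there is no concurrent control group in which the same artefact would appear and cancel. A reader of the tables could take a sampling effect for a drug effect, or discount a real rise as sampling.

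**Working it through.** The plan gives no figure on this point, so there is none to reproduce. The check is a reading of the schedule against the analysis rule.

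**1. Scheduled draws and the fasting rule (Table 1-1, footnotes l and m; Section 6.2)**

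| Visit | Chemistry scheduled | 8-hour fast required |
|---|---|---|
| Week 24/Baseline | yes | yes |
| Weeks 28, 32, 36, 40, 44, 48 | yes (6 draws) | no |
| Week 52/Early Termination | yes | yes |
| Follow-Up | yes | no |

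Total: 1 + 6 + 1 + 1 = 9 draws. Fast required: 2 of 9 (22%). Of the 7 on-treatment draws after Week 24, 6 have no fasting rule.

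**2. Is glucose run at the other seven visits?** Chemistries at each visit, plus glucose in the Chemistry column, means yes on a plain reading. It is not certain. Footnote l lists fasting glucose among additional tests at Weeks 24 and 52, next to hemoglobin A1c. Hemoglobin A1c is also in the Chemistry column, yet the footnote schedules it only at those two visits. The column is therefore not exactly the per-visit panel.

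**3. Are samples at those visits fed?** Not settled either. Section 5.4 has the daily dose taken fasted in the morning, at least 1 hour before breakfast, and taken in clinic only at Week 24/Baseline and Week 52. At the visits between, a patient may dose at home, eat and then attend, or may attend before eating. A mixture is plausible, but its proportions are unknown.

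**4. Illustration of size, on assumed inputs.** If a share *p* of patients is not fasted and a fed sample reads δ higher than a fasted one, the spurious mean shift against a fasted Baseline is p × δ. Neither *p* nor δ is in the document. With δ from 5 to 30 mg/dL:

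- p = 0: 0
- p = 0.25: 1.25 to 7.5 mg/dL
- p = 0.50: 2.5 to 15 mg/dL
- p = 0.75: 3.75 to 22.5 mg/dL

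For scale, split the planned 800 patients equally over three parent groups (an assumption): 800/3 ≈ 267. With an assumed SD of 10 to 20 mg/dL, the 95% confidence half-width of a group mean is 1.96 × 10/√267 = 1.2 to 1.96 × 20/√267 = 2.4 mg/dL. The artefact could exceed sampling error, or be absent. The document does not decide which.

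**5. What stays readable.** The Section 9.5 summaries are by visit, and the synopsis has the laboratory shift tables run from parent study Baseline to each subsequent visit. The protocol-fasted Week 24 and Week 52 results therefore keep their own entries.

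**The case against.** The strongest reply is that this belongs in the SAP. Section 9 leaves detailed methods to it, Section 9.2 carries over the parent studies' methods unless the SAP says otherwise, and the protocol already has fasting status recorded. Nothing in Section 9.5 forbids splitting by that flag. This stands in part: an SAP could repair the analysis. But Section 9.5 does not stay silent. It states a rule for every test at every visit, and followed as written that rule mixes sampling states. The Table 7-2 wording also conflicts with the schedule, whatever the SAP says.

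Other limits stand. The summaries are descriptive, and no stated decision rule uses glucose. The fasting state at parent study Baseline is not given here. Later amendments exist, and their Section 9.5 is not in the pages available.

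A reader might infer three stronger things that the documents do not support:

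- *That glucose will rise at Week 28 and fall at Week 52.* The absence of a fasting rule does not make samples fed, and no figure in the document gives an effect size.
- *That a drug effect on fasting glucose cannot be read at all.* The by-visit layout keeps the two fasted visits separate, with hemoglobin A1c alongside.
- *That high values will be far commoner over Weeks 28 to 48 than at Week 52.* That sets six draws against one, and six draws give more chances of a high value even if all are fasted. Nor does the protocol describe a worst-post-baseline grade table for laboratory values; its maximum-severity rule concerns adverse events.

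Lipids do not share the problem, because they are scheduled only at the two fasting visits.

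**Conclusion.** The point holds as a mismatch between how glucose is sampled and how Section 9.5 says it will be summarized. An 8-hour fast is required at 2 of 9 scheduled draws, and all draws are compared with Baseline and graded alike. Glucose changes and high grades at Weeks 28 to 48 and Follow-Up may reflect sampling state. The conclusion rests on the plain reading that glucose is part of the per-visit panel, and on at least some patients attending fed. Its size cannot be derived from the document; the range in the working is illustrative only. The consequence is confined to a descriptive safety summary, but for a named risk, and correcting it is cheap enough that it should be done.

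**What to change.** - **Section 9.5:** limit glucose change from Baseline, toxicity grading and shift tables to samples recorded as fasted for at least 8 hours on the laboratory requisition, both at parent study Baseline and at the visit concerned. Summarize non-fasted glucose separately, without change from Baseline.
- **Table 1-1, footnote l:** state whether glucose is run at Weeks 28 to 48 and Follow-Up. If it is not, the filter has little to do and the clarification alone settles the matter.
- **Table 7-2:** reconcile the statement that fasting glucose and lipids are done throughout the study with the schedule, which provides them at Week 24/Baseline and Week 52/Early Termination.

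No lipid filter is needed. The cost is wording and one programming filter on a status that Section 6.2 already has recorded. Availability of the same flag at parent study Baseline must be confirmed, since this document does not show it. The downside is fewer glucose time points in the change-from-Baseline table.

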#### Exclusion Criteria

1. Has had a surgical procedure for treatment of endometriosis at any time during the parent study (MVT-601-3101 or MVT-601-3102);
2. Has any chronic pain or frequently recurring pain condition, other than endometriosis, that is treated with opioids or requires analgesics for  $\geq 7$  days per month;
3. Has a weight that exceeds the weight limit of the DXA scanner or has a condition that precludes an adequate DXA measurement at the lumbar spine and proximal femur (eg, bilateral hip replacement, spinal hardware in the lumbar spine);
4. Has a Z-score  $< -2.0$  or has a  $\geq 7\%$  decrease in bone mineral density from the parent study Baseline at lumbar spine, total hip, or femoral neck based on the parent study Week 24 DXA assessment of bone mineral density;
5. Anticipated to use any prohibited medications as detailed in [Section 5.10.1](#);

6. Has any contraindication to treatment with low-dose estradiol and norethindrone acetate, including:
  - a. Known, suspected, or history of breast cancer;
  - b. Known or suspected estrogen-dependent neoplasia;
  - c. Active deep vein thrombosis or pulmonary embolism, or history of these conditions prior to the Week 24/Baseline visit;
  - d. History of or active arterial thromboembolic disease, including stroke and myocardial infarction;
  - e. Known anaphylactic reaction or angioedema or hypersensitivity to estradiol or norethindrone acetate;
  - f. Known protein C, protein S, or antithrombin deficiency, or other known thrombophilia disorders, including Factor V Leiden;
  - g. Migraine with aura;
  - h. History of porphyria;
7. Has current active liver disease from any cause;
8. Has a systemic autoimmune disease (eg, systemic lupus erythematosus, Sjogren's syndrome, rheumatoid arthritis, polymyositis, systemic sclerosis, psoriasis, psoriatic arthritis, vasculitic syndromes, etc); psoriasis not requiring or anticipated to require systemic therapy is permitted;
9. Had any of the following clinical laboratory abnormalities at the parent study Week 20 visit or, if available, any subsequent visit in one of the parent studies (MVT-601-3101 or MVT-601-3102):
  - a. Alanine aminotransferase (ALT) or aspartate aminotransferase (AST) > 2.0 times the upper limit of normal (ULN); or
  - b. Bilirubin (total bilirubin) > 1.5 x ULN (or > 2.0 x ULN if secondary to Gilbert syndrome or pattern consistent with Gilbert syndrome);

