### **6.3. Early Termination Visit and Follow-up Visit**

All patients withdrawing from the study prior to Week 52 will complete an Early Termination visit. The Early Termination visit procedures are identical to those of Week 52; however, for patients whose last dose of study drug is during Week 32 or earlier or within 4 weeks after completion of the Week 36 scan, the bone densitometry does not need to be performed. This procedure may be performed, however, at the investigator's discretion, if it aids in follow-up of an ongoing adverse event(s).

Patients (including those who complete the Week 52 visit and those who withdraw early from this study) will have a Follow-up visit approximately 30 days after the last dose of study drug, or prior to the date of initiation of another investigational agent or hormonal therapy affecting the hypothalamic-pituitary-gonadal axis or surgical intervention or other invasive procedure for endometriosis, whichever occurs first. However, for patients who enroll directly into another relugolix clinical study upon completion of the Week 52 visit, the Follow-up visit may be waived.

The Follow-up visit will be used to assess safety after discontinuation of study treatment including adverse events, clinical safety laboratories, and return of menstruation. Refer to the Schedule of Activities (see [Section 1.1](#)) for individual study visit procedures during the Follow-up visit.

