#### **6.5.2.6. Bone Mineral Density**

Bone mineral density is determined using DXA scanning and will be assessed at the lumbar spine (L1, L2, L3 and L4), total hip, and femoral neck (same leg within each patient) at the time points described in the Schedule of Activities (Section 1.1). The scans will be read by the central imaging laboratory in accordance with the imaging charter. Training, quality review, and readings will be done by a central radiology laboratory as described in the central radiology charter for bone mineral density.

Throughout the study, the same DXA apparatus will be used at each site and operated in the same scan mode for all scans for an individual patient and should be the same as used for the patient during the parent study (MVT-601-3101 and MVT-601-3102). The central core imaging laboratory will collect and evaluate all DXA scans for acceptability. Bone mineral density changes for individual patients will be monitored by the central imaging laboratory over the course of the study.

Patients with a bone mineral density loss of  $> 3\%$  at lumbar spine or total hip at their Week 52/Early Termination visit (or most recent scan if the Week 52/ET scan was not done) relative to parent study Baseline measurement will undergo another bone densitometry scan at  $6 (\pm 1)$  months and will be contacted to obtain information about medications and conditions (eg, pregnancy) that might affect bone mineral density through the time of the follow-up bone densitometry. The follow-up bone densitometry will be submitted for central reading.

Patients who experience a bone mineral density loss from the parent study Baseline of  $\geq 7\%$  at any of the anatomical sites assessed will be discontinued from the extension study and will undergo another bone densitometry scan as described above. Patients should be assessed for secondary causes of bone loss and followed up further if not improving on the 6-month follow-up scan, unless an alternative etiology has been identified.

If the patient enrolls directly into another relugolix clinical study upon completion of the Week 52 visit, then the follow-up bone densitometry scan at  $6 (\pm 1)$  months conducted under this protocol may be waived.

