For vital signs parameters, including temperature, all data will be listed and summarized by visit. The change from parent study Baseline to each post-baseline study visit will be presented by parent study treatment group for each parameter.

Clinical laboratory data consist of chemistry, hematology, and hormonal tests. Only data collected by the central laboratory will be used to do the analyses. ECGs will also be read centrally. The distributions of QTc interval will be summarized at each visit. All data will be listed and summarized by visit. The change from parent study Baseline to each post-baseline study visit will be presented by treatment group for each ECG parameter.

The incidence of vasomotor symptoms as assessed through adverse event reporting will be summarized by the parent study treatment arm.

Bone mineral density data will be collected and analyzed by the central radiology laboratory including bone mineral content (g), bone area (area, cm^2), and bone mineral density (g/cm^2) each for L1, L2, L3, L4, total hip, and femoral neck, and average bone mineral density of L1-L4 (lumbar spine), Z-score for bone mineral density lumbar spine (L1-L4), total hip, and femoral neck.

For the relugolix add-back treatment Group A, the lower bound of the 95% CI for (arithmetic) mean percentage change at Week 52 from parent study Baseline in bone mineral density lumbar spine (L1-L4) will be compared with a pre-specified clinically acceptable threshold of -2.2% to evaluate magnitude of bone mineral density loss after 52 weeks of treatment. If the lower bound is > -2.2%, the bone mineral density loss for the relugolix add-back treatment will be considered insignificant. As supportive analysis, least square means and 95% CI for percent change at Week 52 from parent study Baseline in bone mineral density will be provided based on mixed effects model (assumed missing at random) for each parent study treatment group.

All data will be listed and summarized by visit. The absolute change and percent change from parent study Baseline to Weeks 36 and 52 and associated 95% CIs will be presented by the parent study treatment group for each bone mineral density parameter. The number and percentage of patients meeting a bone mineral density decline of at least 4%, 5%, 6%, or 7% by body area (lumbar spine, total hip, or femoral neck) will be estimated with 95% CIs by the parent study treatment group.

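### The -2.2% lumbar-spine verdict rests on the plain Week 52 mean, which leaves out women removed for 7% or more bone loss; the mixed model already planned should carry the decision

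*Protocol*

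**What the plan says.** Section 9.5 fixes the decision statistic for Group A as "the lower bound of the 95% CI for (arithmetic) mean percentage change at Week 52 from parent study Baseline in bone mineral density", taken at the lumbar spine. This bound is "compared with a pre-specified clinically acceptable threshold of -2.2% to evaluate magnitude of bone mineral density loss after 52 weeks of treatment". A bound above the threshold leads to the conclusion that "the bone mineral density loss for the relugolix add-back treatment will be considered insignificant". The same paragraph adds, as supportive only, least squares means and 95% CIs "based on mixed effects model (assumed missing at random) for each parent study treatment group". The original protocol states the rule in the same terms.

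Four other provisions decide who can contribute to that mean:

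- **Entry.** Exclusion criterion 4 (Section 4.3.1) bars women whose scan shows a 7% or greater "decrease in bone mineral density from the parent study Baseline at lumbar spine, total hip, or femoral neck based on the parent study Week 24".
- **Removal.** Sections 4.5 and 6.5.2.6 remove women on study. Under the latter, women with a 7% or greater loss "at any of the anatomical sites assessed will be discontinued from the extension study".
- **Scan waiver.** Under Section 6.3 and footnote q of the Schedule of Activities, if the last dose falls "within 4 weeks after completion of the Week 36 scan, the bone densitometry does not need to be performed".
- **Time point.** The bone density endpoint in Section 3 is set at Week 52, whereas most efficacy endpoints are set at Week 52/EOT.

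The population is described in two ways. The Synopsis applies the rule to Group A women who enrolled in the extension. Section 9.2 defines the Safety Population as all women randomized and dosed in a parent study.

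**The concern.** Women leave on the same outcome that is being averaged, and always from the unfavourable tail. A woman stopped on her Week 36 result has no Week 52 value, and nothing in the protocol text brings her last scan into the mean. The trigger is a recorded scan. That is the setting in which a likelihood model using the earlier scans is approximately valid and an observed-case mean is not. The protocol plans both and lets the second decide.

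At stake is the only numerical pass/fail criterion in the efficacy and safety analyses shown. Its conclusion is worded for the treatment as a whole, not for women who stayed to Week 52.

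**Working it through.** **1. The plan's own figure.** 0.67 x 1200 = 804 and 800/1200 = 66.7%, so the planned enrolment of about 800 reproduces. The allocation ratio is not stated. Assuming 1:1:1, Group A is 400 dosed and about 267 enrolled. No SD, expected mean or power is given for the -2.2% rule.

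**2. Precision.** The CI half-width is 1.96 x SD/sqrt(267). At SD 2.5% it is 0.30 points and at SD 3% it is 0.36, so the mean must be better than about -1.90 or -1.84 to pass. Shifts of 0.1 to 0.4 points are therefore not negligible.

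**3. Order of magnitude.** If every woman with a Week 52 spine value at or below -7% were missing, the mean would shift by SD x phi(a)/(1 - Phi(a)), with a = (-7 - mean)/SD. At a true mean of -2.2%:
- SD 2.5: a = -1.92, 2.74% of women affected, shift 0.16.
- SD 3: a = -1.60, 5.48% affected, shift 0.35.

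The real selection acts on earlier, correlated scans, but at three sites and two visits. It needs simulation.

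**4. Simulation.** All of these inputs are assumptions: 400 Group A women; 72% of eligible women enrol; 12% unrelated dropout; 60, 80 and 100% of the mean loss reached at Weeks 24, 36 and 52; time correlation 0.7; site correlation 0.5; femoral neck at the SD shown and total hip at 0.85 times it. The 7% rule is applied at any site at Weeks 24 and 36. The true Week 52 mean in all dosed women is -2.2%.

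| Assumed SD (%) | 2.0 | 2.5 | 3.0 |
|---|---|---|---|
| Mean of enrolled women, had all been followed | -2.18 | -2.12 | -1.99 |
| Mean of women with a Week 52 scan | -2.16 | -2.04 | -1.83 |
| Shift against enrolled women | 0.02 | 0.08 | 0.17 |
| Shift against all dosed women | 0.04 | 0.16 | 0.37 |
| Passes (nominal 2.5%) | about 5% | about 18% | about 50% |

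The means carry simulation error of about 0.01. A likelihood estimate using the Week 24 and Week 36 spine scans of all dosed women recovers about -2.20 and passes in 2 to 3% of trials. If the enrolled women's own mean is placed at -2.2%, the observed-case rule stays close to nominal at SD 2 and passes in about 8% and 18% of trials at SD 2.5 and 3.

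**5. Sensitivity to the assumptions.** A second set of visit and site correlations, with 20% unrelated non-enrolment and 10% dropout, gives 12% and 35% passes at SD 2.5 and 3. The likelihood estimate again gives 2.4 to 2.5%.

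**6. Counting the last scan.** Under that second set, treating the Week 36 scan of removed women as their Week 52 value cuts the passes to 3% and 6%. The means become -2.18 and -2.13. For enrolled women the target is -2.16 and -2.08, so this device slightly overshoots that target while falling short of -2.2%.

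**7. Away from the margin.** At a true mean of -1.0%, the observed mean is shifted by 0.05 and 0.16 points at SD 2.5 and 3 (second set). The rule passes in essentially 100% of trials with or without the selection. At a true -2.0% and SD 3% (first set), pass rates are 81% for the observed-case mean and 21% for the likelihood estimate.

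**The case against.** **Population.** The Synopsis names enrolled women. For that set the Week 24 bar limits generalization and is not bias. This stands: about half the shift in the table (0.08 of 0.16 at SD 2.5, 0.21 of 0.37 at SD 3) comes from entry. What remains is the effect of removal at Week 36, plus a verdict worded more broadly than the enrolled set.

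**Size.** The documents give no SD, so a reader should not infer a known, inflated error rate from the 5 to 50% range. At SD 2% the effect is small, and if the true loss is around 1% the verdict is the same either way.

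**Partial safeguards.** The mixed model and the Week 36 summaries will be reported, so a discrepancy would be visible. The early-termination scan is waived, not forbidden, and the SAP, which is not at hand, may map such scans to Week 52. These points reduce the problem. They do not change which statistic decides.

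**The remedy is not exact.** Hip or femoral-neck loss also triggers removal, so a spine-only model is only approximately valid under missing at random. With a constant cross-site correlation of 0.5, the likelihood mean is -2.18 and -2.15 at SD 2.5 and 3, with 3.4% and 4.7% passes. That is much closer to nominal than the observed-case mean.

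**Decline categories.** One might infer that the tabulated declines of 4 to 7% share the defect. Section 9.5 ties those counts to no visit, so the text does not support that.

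**Version.** The wording is that of the original protocol and Amendment 1. Section 9.5 of the later amendments is not in the part available, so whether the rule survived is unknown.

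**Conclusion.** As written in Amendment 1, the rule decides on the more selected of two planned estimates. The direction, toward less apparent loss, follows from the removal rules. Among enrolled Group A women the shift is modest, about 0.02 to 0.17 points for SDs of 2 to 3%. Against all dosed Group A women it is about 0.04 to 0.37 points, with about 5 to 50% passes at a true -2.2%. These sizes depend on the assumed SDs, correlations, allocation and dropout.

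The documents do not show that a favourable verdict would be wrong. They show that the rule is least reliable where the true loss is near the margin, which is where a margin has to work.

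**What to change.** In Section 9.5 and the Synopsis, apply the -2.2% criterion to the Week 52 least squares mean and lower 95% bound from the planned mixed model. Fit it to all parent and extension lumbar-spine scans, including the last scans of women removed for bone loss, each entered at its own visit. Keep the arithmetic mean as supportive.

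State which Group A women the rule covers, so that the Synopsis and Section 9.2 agree. If the conclusion is to speak for the add-back treatment as a whole, fit the model to all dosed Group A women. If it is to speak for enrolled women only, word the conclusion accordingly.

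No clinical removal rule needs to change. The cost is a revised decision sentence in two places and a settled population; the model is already planned. The downside is a slightly less favourable figure and reliance on an approximate missing-at-random assumption. If later amendments kept the rule, the same change belongs in the version in force.
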